|              | Controls                             | 250                                     | 750                                     | 1250                                    | 1500                                    |       |
| Total | Cases                         | 3550                                    | 9700                                    | 15850                                   | 19500                                   | 34500 |
|              | Controls                      | 2950                                    | 7500                                    | 12050                                   | 15000                                   |       |

**5.5. List inclusion and exclusion criteria, including age ranges of all participants, and describe the screening process. Provide a rationale for any specific exclusion criteria.**

All the sites from five countries use the same recruitment protocol to ensure study consistency. Potential cases will be recruited from outpatient and inpatient clinics with the following inclusion criteria:

1. Any subjects who meet DSM-5 the diagnostic criteria for Bipolar I Disorder;
2. Age at recruitment is 18-75 years old
3. Age of the first episode (either major depressive episode or manic episode) prior to age 50;
4. At least three years since the initial diagnosis of Bipolar Disorder.

Cases will be excluded if:

1. Persons who are currently involuntarily detained
2. Persons who are currently acutely psychiatrically illness
3. Anyone whose treating physician believes that participation could be harmful to them
4. Any history of a psychiatric illness caused by a neurologic condition (including mental disorders caused by epilepsy, cerebral tumor, CNS infections, or head trauma)

5. Any history of moderate or severe intellectual disability
6. Any history of a diagnosis of a mental disorder secondary drug or alcohol use

Selected controls will be recruited at each site and matched on ascertainment location, ethnicity, age at ascertainment and sex. Controls will be recruited following the inclusion criteria below:

1. Any subjects who screens negative for bipolar disorder I or II, schizoaffective disorder and schizophrenia
2. Age at recruitment is 18-75 years old

Exclusion criteria of controls are:

1. Any history of mania or psychosis or diagnosis of any DSM-5 bipolar diagnosis or psychotic disorder

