2. Any history of a psychiatric illness caused by a neurologic condition (including mental disorders caused by epilepsy, cerebral tumor, CNS infections, or head trauma)
3. Any history of moderate or severe intellectual disability
4. Any history of a diagnosis of a mental disorder secondary to drug or alcohol use.

Note that a diagnosis of major depressive disorder (without psychosis) or a diagnosis of a substance use disorder itself will not be exclusion criteria for controls in order to avoid biases in our genetic findings with signals related to these relatively common conditions.

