**Rationales for exclusion criteria in cases:**

1. We excluded the patients who are involuntarily detained in the hospital to make sure there's no coercion in participating the study
2. For the safety and wellness of patients, those who are under acute illness will be excluded from the study
3. Premorbid mental disorders and previous history of drug use are excluded to eliminate the confounding factors in the analysis.

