**Taiwan Recruitment**

All recruitment conversations are done in the potential participant's preferred language by a research assistant or study nurse, either in Mandarin Chinese or Taiwanese language. We enroll Taiwanese Han Chinese with both genders in this study. We plan to recruit 3000 cases and 1500 controls in total over four years. Because Taiwan legal adult age is set at 20 y.o., therefore, only adult men and women between 20 and 70 will be recruited within this study. Recruitment materials include flyers and posters of both hard copy format and electronic file format for social media recruitment. Flyers are present in Mandarin Chinese and containing

brief information about the study, inclusion/exclusion criteria are shown in the following section. Contact and more detailed information will be explained to patients by research assistants or psychiatrists. The target number of participants was carefully calculated based on estimated caseloads of patients with the diagnoses of interest in each of the study sites following several discussions with clinicians who practice at the study sites. We estimate approximately 50% participation rate, because participation is relatively slight-impact. In addition, we will re-contact patients (500~) and controls (500~) who participated in previous studies to invite them to join the proposed project. Those who agree to participate will re-sign the informed consent.

Cases – Patients with bipolar I disorder, or schizoaffective disorder-mania type are recruited primarily from clinical settings from both inpatient and outpatient facilities in central and regional hospitals. Patients will be recruited in the Northern, Central, Southern, and East-coast cities. In out-patient departments, psychiatrists briefly introduce the study to eligible patients, if patients are willing to join the study, then 1) referral to the research assistants to introduce the details of the study and sign the informed consents. 2) leave the contact information, the research assistants will contact them within seven days. For psychiatric inpatients, patients will be referred to a study assistant by psychiatrists when their mood is relatively stable. The study assistant introduces the details of the study and signs an informed consent in the ward, the detailed interview will be after the day of discharge. Cases are recruited predominantly on clinics and wards from a network of university hospitals in the four main regions in Taiwan.

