Inclusion and exclusion criteria for cases: consistent with the study criteria and we will additionally exclude cases with substance induced bipolar disorder, mental retardation, schizophrenia, dementia, and HIV infection. Aboriginal in Taiwan will be excluded since our main target population is Han Chinese.

Controls - We ascertain controls from persons who present for treatment of general medical conditions at general medical hospitals that draw from similar catchment areas to the psychiatric facilities, as well as community controls. Controls must screen free from any psychiatric disorders history. We also use flyers of both hard copy format and electronic file format for social media recruitment. Willingness participants from social media actively contact and leave the message to the study team, study assistants will contact them to introduce the details of study and sign the informed consent and interview questionnaires. The local study team is the first point of contact for the patient and will explain the study and enroll controls into the study.

Inclusion and exclusion criteria for controls: consistent with the study criteria. Aboriginal in Taiwan will be excluded since our main target are Han Chinese

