### **Korea Recruitment**

Cases: We will recruit 4000 bipolar I patients in clinical settings from both inpatient and outpatient facilities. No cases will be enrolled or interviewed when they are currently an inpatient and cases will only be approached on the day of discharge. All participants are over 18 years of age. Both males and females will be recruited in the study. All recruitment conversations are done by psychiatrists. Recruitment materials include flyers and posters. Flyers containing brief information about the study, inclusion/exclusion criteria and study contact information are handed out by the research staff to potential participants. The local study team is the first point of contact for the patient and explains the study and enrolls patients into the study.

Controls: We ascertain controls from persons who present for treatment of general medical conditions at general medical hospitals within similar catchment areas to the psychiatric facilities where cases are recruited. These individuals will be screened according to the overall study inclusion/exclusion criteria.

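### Taiwan's control screen contradicts the study-wide control criteria and, if applied as written, over-screens controls in one country only

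*Protocol*

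**What the plan says.** Section 5.5 of the protocol opens its eligibility criteria with "All the sites from five countries use the same recruitment protocol to ensure study consistency". After the control exclusions it adds that "a diagnosis of major depressive disorder (without psychosis) or a diagnosis of a substance use disorder itself will not be exclusion criteria for controls", and gives the reason: "in order to avoid biases in our genetic findings with signals related to these relatively common conditions".

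Section 6.1, Taiwan Recruitment, says of controls: "Controls must screen free from any psychiatric disorders history". The same subsection then states "Inclusion and exclusion criteria for controls: consistent with the study criteria" and names only one further control exclusion, aboriginal ancestry. The Taiwan target is given as "We plan to recruit 3000 cases and 1500 controls in total over four years".

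Singapore's controls follow the study criteria. For Korea the text says "These individuals will be screened according to the overall study inclusion/exclusion criteria".

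On the case side, exclusion 6 in section 5.5 covers a mental disorder secondary to drug or alcohol use. The third rationale in the same section is wider: "Premorbid mental disorders and previous history of drug use are excluded to eliminate the confounding factors in the analysis".

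**The concern.** Someone with non-psychotic major depression or a substance use disorder is an eligible control under section 5.5 and an ineligible one under the Taiwan sentence. The protocol gives its own reason why that matters. If these common conditions are removed from controls but left in cases, the case-control contrast picks up alleles for depression and substance use as well as alleles for BP-I.

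The numbered case criteria do not exclude comorbid substance use disorder as such, and case inclusion 3 accepts a depressive first episode. The added Taiwan case exclusions include substance-induced bipolar disorder, but not substance use disorder or depression.

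Aim 3 compares genetic architecture across populations and across disorders. A selection effect confined to one country is most awkward there, because it can pass for a real difference between countries. Section 6.1 also places Taiwan among the three sites that start enrolment first, and eligible controls who are turned away cannot be recovered at analysis.

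**Working it through.** **Texts side by side**

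| Place | Control with non-psychotic depression or substance use disorder |
|---|---|
| Section 5.5, note on controls | eligible, to avoid bias |
| Section 5.5, opening | same protocol at every site |
| Section 6.1, Taiwan, screening sentence | not eligible |
| Section 6.1, Taiwan, criteria line | as study criteria, so eligible |
| Section 6.1, Singapore and Korea | as study criteria, so eligible |

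Taiwan's extra case exclusions are announced as additional. The stricter control screen is not, and no reason is given for it.

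**Taiwan's weight.** The section 5.4 site targets add up as stated:
- Cases: 2,000 + 10,000 + 4,000 + 500 + 3,000 = 19,500.
- Controls: 1,000 + 10,000 + 2,000 + 500 + 1,500 = 15,000.

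Taiwan has 1,500/15,000 = 10.0% of controls and 3,000/19,500 = 15.4% of cases. Effective sample size per country is 4/(1/cases + 1/controls): Japan 2,667, India 20,000, Korea 5,333, Singapore 1,000, Taiwan 4,000, total 33,000. Taiwan's share is 4,000/33,000 = 12.1%, or 4,000/13,000 = 30.8% of the four countries other than India.

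**Shift per variant.** Let K be the share of eligible controls with the condition, and take a variant with an allelic odds ratio for that condition but no effect on BP-I. The population allele frequency is f = K × f(affected) + (1 − K) × f(unaffected). Cases carry f and screened controls carry f(unaffected), so the spurious odds ratio is odds(f)/odds(f(unaffected)), close to OR^K. K, OR and f are not in the protocol and are assumed here, with f = 0.30.

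| K | OR for condition | Spurious OR, Taiwan | z, Taiwan alone | Diluted over five countries |
|---|---|---|---|---|
| 5% | 1.05 | 1.002 | 0.05 | 1.0003 |
| 15% | 1.10 | 1.015 | 0.30 | 1.002 |
| 30% | 1.20 | 1.058 | 1.14 | 1.007 |

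z is ln(spurious OR) divided by the allelic standard error for 3,000 cases and 1,500 controls. The last column weights the log odds ratio by 12.1%. At these values of K, the screen removes 75 to 450 of every 1,500 people who would qualify under section 5.5.

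**Polygenic effect.** This uses a liability-threshold model with the true genetic correlation set to zero, to isolate the spurious part.
- Mean liability shift in screened controls, s = φ(t)/(1 − K): 0.109 at K = 5% and 0.274 at K = 15%.
- BP case-control liability contrast, i = φ(t)/[P(1 − P)]: 2.69 at prevalence P = 1% and 2.47 at 2%. Section 2.1 gives 1 to 2%.
- Spurious correlation = s√r/√(i² + s²r), where r is the ratio of SNP heritabilities, assumed 0.5 to 1.
- Low end: 0.109 × 0.707 = 0.077, and 0.077/√(2.69² + 0.077²) = 0.029.
- High end (r = 1): 0.274/√(2.47² + 0.274²) = 0.110.

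The range in the Taiwan stratum is therefore about 0.03 to 0.11. Weighted by 12.1% it is roughly 0.003 to 0.013 for the five countries together.

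**The case against.** The best defence is that the Taiwan sentence may be a loose paraphrase of the study rule that controls screen negative for bipolar and psychotic disorders. The line stating consistency with the study criteria would then be the operative one. The plain words do not say that, but the document does not settle it. A reader might infer that the Taiwan contrast certainly carries the bias. It does so only if the sentence is applied as written.

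A reader might also infer false BP-I loci. The arithmetic does not support this: an expected z of 0.05 to 1.14 is far too small. Nor does Taiwan amount to a third of controls. That figure comes from setting 1,500 against the 4,500 in Japan, Korea and Taiwan, which leaves out India and Singapore. Treating any psychiatric disorder as one trait of 20 to 30% prevalence would give 0.09 to 0.20, but that does not measure the bias for depression or substance use individually.

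The rationale sentence about previous drug use could be read as biasing the substance-use comparison at every site. The numbered criteria set eligibility, however, and they are narrower. Applied literally together with the Taiwan screen, the rationale would make Taiwan's substance-use contrast more symmetric, not less. The depression asymmetry would remain, because case inclusion 3 accepts a depressive onset.

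Finally, section 5.6 collects reports of past psychiatric diagnoses from all participants, so a common control filter can be applied at analysis, and an SAP that is not shown may provide for one. This mitigates the problem but does not remove the contradiction. It also cannot restore controls who were never enrolled.

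**Conclusion.** The contradiction is certain: the Taiwan screening sentence conflicts with the section 5.5 note, with the uniform-protocol statement and with Taiwan's own criteria line. The bias is conditional on that sentence being applied. Its direction follows from the protocol's own reasoning and holds for any condition prevalence above zero. Its size rests on assumed prevalences, effect sizes and heritability ratios; only the BP prevalence and the sample sizes come from the document.

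On those assumptions the effect is negligible for single variants and small in the pooled study. It is large enough to matter in Taiwan-specific polygenic, cross-disorder and between-country comparisons. It should be corrected at the source, preferably before Taiwan's early enrolment goes further. The mismatch between rationale 3 and case exclusion 6 is a secondary point of wording.

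**What to change.** 1. Delete the Taiwan sentence requiring controls to be free of any psychiatric history, so that the section 5.5 control criteria apply there unchanged. If the site has a reason to keep the screen, declare it as a departure, justify it, and remove the statement that its criteria match the study's.
2. Establish how Taiwan controls already enrolled were screened, and what screen the roughly 500 re-contacted controls passed in their earlier studies. At 500 of 1,500 they could be a third of Taiwan's controls, and rewording does not undo earlier selection. Flag any who passed a stricter screen.
3. Run the cross-disorder and between-country analyses with and without flagged controls, or with one control filter applied at every site using the past-diagnosis reports from section 5.6.
4. Reword rationale 3 in section 5.5 to match case exclusion 6.

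The cost is two wording changes with Taiwan and Harvard IRB amendments, a check of the earlier studies' screening records, and one sensitivity analysis. Control recruitment in Taiwan becomes slightly easier.

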### **Korea Recruitment**

Cases: We will recruit 4000 bipolar I patients in clinical settings from both inpatient and outpatient facilities. No cases will be enrolled or interviewed when they are currently an inpatient and cases will only be approached on the day of discharge. All participants are over 18 years of age. Both males and females will be recruited in the study. All recruitment conversations are done by psychiatrists. Recruitment materials include flyers and posters. Flyers containing brief information about the study, inclusion/exclusion criteria and study contact information are handed out by the research staff to potential participants. The local study team is the first point of contact for the patient and explains the study and enrolls patients into the study.

Controls: We ascertain controls from persons who present for treatment of general medical conditions at general medical hospitals within similar catchment areas to the psychiatric facilities where cases are recruited. These individuals will be screened according to the overall study inclusion/exclusion criteria.

## 7. Consent Process

*Upload consent form(s) and debriefing materials, if applicable, to the “Local-Site Documents” page in ESTR.*

### 7.1. Describe how the research team will invite participants to take part in the research and obtain consent to participate. If the research team will not obtain informed consent, provide justification for requesting a waiver or alteration of consent (and/or parental permission).

Informed consent will be obtained for all adult participants who are participating in the studies. When conducting the informed consent process with study participants, trained research staff will determine the individual’s level of comprehension of the material presented, based on whether the subjects are able to paraphrase the information in the consent form, to comprehend it adequately, and to ask reasonable questions about their participation. Any participant who does not demonstrate adequate understanding of the purpose, procedures, risks, benefits, emergency contacts, and payment issues will not be allowed to participate. All participants will be given a verbal explanation of the study purpose, procedures, risks, benefits, and payment and reminded that their participation is voluntary. Subjects who wish to do so will be encouraged to speak with their family members, friends, and physicians and show the consent form to them before making their decision to participate. The procedures are straightforward and outlined clearly in the informed consent process. After reading the consent forms or having assent forms explained, participants will be asked to provide a statement of their understanding of the research, the research procedure, any risks or discomfort involved, possible benefits of the study, and their right to withdraw at any time. If a participant indicates inability to comprehend provided material or is judged to be unable to comprehend this material, that individual will not be permitted to participate in the research. Once the participant confirms comprehension of the consent form and all study procedures, and agrees to participate he/she will be asked to sign the consent form.

- 7.2. Describe how the research team will document the consent process (e.g., participant/researcher will both sign and date the consent document; participants will thumbprint the consent document; electronic consent will be obtained and associated with the participant’s research record). If the research team will not obtain signature and date, provide justification for requesting a waiver or alteration of documentation of consent (and/or parental permission).**

We will use the paper consent form. Participant and researcher will both sign and date on the consent document. For participants who are illiterate, participants will fingerprint the consent document and researchers will write printed names and date for them. The consent process will be documented on the study enrollment log.

- 7.3. Will participants be offered a copy of the consent information?**

Yes  No: *If no, explain why not.*

- 7.4. If consent will be obtained in a language other than English, identify the language(s) that consent information will be provided, who will be responsible for translation, and the provisions for communicating this information to participants.  N/A**

All consent forms will be in their native languages. For example, consents in Japan will be in Japanese; consents in Singapore will be in English, Chinese and Tamil; consents in India will be in Kannada, Tamil, Hindi, Telugu, Malayalam depending on the cities; consents in Taiwan will be in Mandarin Chinese or Taiwanese. All consenting conversations will happen in participants' preferred language in local hospitals/institutions.

The translation will be done jointly between Broad Institute investigators and site investigators, and the consent form will be submitted for local IRB review.

- 7.5. If the research involves deception and/or incomplete disclosure, describe the debriefing process. Explain when participants will be debriefed, who will debrief them, and how they will be debriefed.  N/A**

- 7.6. If the research involves secondary use of existing data, documents, records, and/or specimens, and the research team will not obtain consent, describe how consent was originally obtained. Additionally, either upload the original consent form to the ESTR record or confirm that the original consent process obtained participants’ permission to share or use their data/specimens for future research projects.  N/A**

- 8. HIPAA Privacy Protections  N/A. Skip to next section.**

*HIPAA applies to US-based research involving the collection or use of protected health information (PHI) from a hospital, health center (including the Harvard Dental Center), health plan, or health insurance plan (i.e. a covered entity). The Privacy Rule will not directly regulate researchers who are engaged in research within organizations that are not covered entities even*

*though they may gather, generate, access, and share personal health information (PHI). The Privacy Rule applies only to individually identifiable health information held or maintained by a covered entity. Individually identifiable health information that is held by anyone other than a covered entity, including an independent researcher who is not a covered entity, is not protected by the Privacy Rule and may be used or disclosed without regard to the Privacy Rule.*

